APPENDIX 1 – SCHEDULE OF STUDY ASSESSMENTS

APPENDIX 2 – INVESTIGATIONAL SITE LIST

APPENDIX 3 – DEFINITIONS

PROTOCOL SUMMARY

| | |
|--|--|
| Study Title: | Prospective Randomized Trial Comparing the Safety and Performance of the Interscope EndoRotor® Mucosal Resection System with Continued Ablative Therapy in Subjects with Refractory Dysplastic Barrett's |
| Protocol No. | CLIN 0010 / D |
| Study Design: | A prospective, multi-center, randomized trial to compare the safety and performance of the Interscope EndoRotor® Mucosal Resection System in subjects with refractory dysplastic Barrett's Esophagus |
| Patient Population: | Subjects with refractory Barrett's metaplasia after 3 failed radiofrequency ablations (RFA) |
| Primary Objective: | To evaluate the EndoRotor®'s ability to completely remove areas of Barrett's metaplasia considered refractory after 3 failed radiofrequency ablations (RFA). |
| Secondary Objectives: | 
1. To compare the EndoRotor® to standard of care ablative therapies by determining the percent reduction of activated fibroblasts in the region of resection and ablation, respectively.2. Assessment of post procedure pain (chest pain discomfort events requiring narcotic analgesic). |
| Primary Endpoints: | Primary Effectiveness Endpoint: Complete removal of areas of Barrett's metaplasia after no more than two treatments. Primary Safety Endpoint: Assessment of Adverse Events (incidence, relationship to device and severity) compared to the control arm and the medical literature. |
| Secondary Endpoint: | Percent reduction of the area with Barrett's esophagus that was resected or ablated during the initial treatment session through the final follow-up visits. |
| EndoRotor® Arm | Once final study eligibility has been confirmed (i.e. after 3 failed radiofrequency ablations (RFA), the patient will receive the EndoRotor® device. |
| Continued Ablative Therapy Arm: | The EndoRotor® will be compared to continued standard of care ablative therapies with currently available Radio Frequency Ablation (RFA) treatments and/or cryotherapy ablation with cleared cryotherapy devices. |
| Study Duration: | Subjects will be followed with biopsies of the resected areas at the time of surveillance endoscopies every 3 months until they have 2 consecutive negative endoscopies and biopsies (6 months) |
| Clinical Sites: | A minimum of 3 and up to 5 sites in the United States will enroll subjects. |

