4.4 Secondary Endpoint

Percentage of Barrett's esophagus resected or ablated during the initial treatment session through the final follow-up visits.

The secondary effectiveness endpoint will be measured by post-treatment visual appearance on surveillance endoscopies and the findings on histology from biopsies taken of the treatment site at each endoscopy.

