5.5.3 Index Procedure

Once enrolled, each patient will be randomized into either the EndoRotor® mucosal resection arm or the control ablation arm. Randomization will occur within 2 weeks of the procedure. The investigators shall follow the technique described by the manufacturer's instructions as provided in the Instructions for Use.

Endoscopic treatment of the esophagus will be performed within 6 weeks of enrollment with outpatient video documentation of the residual Barrett's changes during upper endoscopy.

EndoRotor® Arm: At this point, the EndoRotor® will be set-up and used to resect the mucosa and submucosa to remove all gross visible disease. Lesions will be "lifted" using saline solution with dye such as Indigo carmine or Methylene Blue. Indelible ink (such as SPOT) will be injected into the region of the resection to identify the site after resection. If the lesion is circumferential, the endoscopist shall resect no greater than 270 degrees of the radial circumference of the esophagus to avoid stricture formation. The resection is taken down to the muscularis propria layer to ensure all of the mucosa and submucosa is removed in the area of persistence.

The EndoRotor® is set to either High Speed (1700 RPM) or low speed (1000 RPM) based on user preference and the vacuum is set to between 250 mmHg and 350 mmHg of negative pressure. The endoscopist will start the EndoRotor® motor using the left foot pedal, and will activate the cutting by depressing and holding the

right pedal down for as long as he wants to resect tissue. The procedure is repeated until the entire gross visible lesion has been removed down to the muscularis propria without entering the muscle layer. The specimen can be sent to Pathology by removing the filter in the specimen trap. A new filter is placed in the specimen trap allowing multiple lesions to be treated and analyzed histopathologically.

Continued Ablative Therapy Arm: The investigator shall exercise standard of care for continued ablative therapies namely RFA (HALO 90/60) and/or cleared cryotherapy devices. These will constitute two control devices. The investigator will choose the system in this arm. Operation of the each system will be done according to the manufacturer's instructions for use. The type of system used will be indicated on the case report forms.

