5.6 Follow-Up Procedures and Therapy Transitions

Surveillance endoscopy is performed in 3 months where there is visual inspection of the treated areas. Biopsies are taken from the areas treated with the respective device are sent to pathology to evaluate for the presence of intestinal metaplasia (Barrett's). If the samples are read as negative by Pathology (no Barrett's seen), the patient then undergoes another endoscopy in 3 months. If the results again are negative, the patient is declared to have a complete response to the treatment (EndoRotor® or ablative therapy).

If there is intestinal metaplasia (Barrett's) confirmed by the biopsy, the patient undergoes a second treatment with either the EndoRotor® or ablative therapy as described in Section 5.7. Two consecutive negative results at 3 month intervals between biopsies is required to consider these subjects complete responders.

If there is intestinal metaplasia (Barrett's) seen either at 90 days or at 180 days after either (EndoRotor® or cryotherapy / ablative therapy) second treatment, the patient is considered to have failed and will exit the study.

To evaluate the secondary endpoint of this study, "Percent reduction of the area with Barrett's esophagus that was resected or ablated during the initial treatment session through the final follow-up visits", percent reduction of the area with Barrett's esophagus will be determined by a decrease in overall length. Using the Prague criteria, both the circumference and maximal length of the Barrett's segment will be estimated. A percentage reduction in the length will be calculated by length measured at the follow up endoscopy divided by the total prior length.

Adverse events, as defined in Section 10.4, will be recorded from the index procedure (Day 0) through study completion and/or exit/withdrawal.

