5.8 Laboratory Testing Procedures

5.8.1 Specimen Preparation (EndoRotor® Arm Only)

The EndoRotor® specimen trap has a 1 micron filter that can be replaced once the lesion is fully removed. The trap is opened and the filter is removed and placed into a small jar with 10% formalin and then is sent to Pathology for histologic evaluation. Samples will be labeled in a blinded manner before being sent to pathology; however, it should be noted that ablative therapies do not allow for retrieval of pathology. Therefore, only the EndoRotor will include pathology from actual procedure.

Surveillance endoscopy biopsies will be obtained using standard endo-forceps and will be sent to Pathology in small jars of 10% formalin. Using the Prague Criteria to assess lesions that were previously treated the lesion can be biopsied using the Seattle Protocol which requires 4 quadrant biopsies per 1cm of length in the involved segment according to the standard of care for follow-up endoscopy. In the case of patients receiving EndoRotor treatments the patients are only receiving treatment on up to 270 degrees of surface area to avoid risk of stricture. Therefore, only positive biopsies in the EndoRotor® treated segment will be considered for further ablation. If biopsies in the EndoRotor treated section are negative they will continue with the follow-up endoscopy of the protocol until a second negative endoscopy according to the follow-up protocol. In a subset of the first 5 subjects (n=5), abnormal submucosal glands and fibroblasts will be harvested to determine the activity of cancer-associated fibroblasts in the submucosa before and after use of the EndoRotor® device. Dysplasia associated fibroblasts will be identified by their association with irregular shaped glands by Volume Laser Endomicroscopy. The areas will be marked using the laser marking device available on the VLE device.

After marking the areas with the system using two marks approximately a centimeter apart, the targeted area will be biopsied twice using a "keyhole" technique. This will ensure acquisition of the appropriate submucosal tissue.

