7.6 Effectiveness Hypotheses

Primary Endpoint Hypothesis 1 (non-inferiority): It is hypothesized that EndoRotor® will not have fewer subjects with complete removal than those treated with control.

$$\begin{array}{ll} \text{Null Hypothesis:} & nE - \delta \leq nC \\ \text{Alternate Hypothesis:} & nE - \delta > nC \end{array}$$

Where nE =Proportion with successful treatment in EndoRotor® arm; nC = proportion with successful treatment in the control arm and δ is a non-inferiority margin of 10% (which is subtracted from nE).

Primary Endpoint Hypothesis 2 (superiority): The proportion of subjects with successful eradication areas of Barrett's metaplasia will be greater for those treated with EndoRotor® than for those treated with control.

$$\begin{aligned} \text{Null Hypothesis: } & nE \leq nC \\ \text{Alternate Hypothesis: } & nE > nC \end{aligned}$$

Where nE =Proportion with successful treatment in EndoRotor® arm; nC = proportion with successful treatment in the control arm.

Secondary Endpoint Hypothesis: The percentage tissue removal of Barrett's metaplasia will be greater for those treated with EndoRotor® than for those treated with control.

$$\begin{aligned} \text{Null Hypothesis: } & \mu E \leq \mu C \\ \text{Alternate Hypothesis: } & \mu E > \mu C \end{aligned}$$

Where μE =mean % tissue removal for EndoRotor® arm; μC = mean % tissue removal for control arm.

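### The secondary endpoint is named as reduction in Barrett's area but scored by length, which can read 0% after a clean 270-degree resection of a circumferential segment

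*Combined protocol and SAP*

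**What the plan says.** The endpoint is worded in several ways.

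- Protocol Summary, repeated in section 5.6: "Percent reduction of the area with Barrett's esophagus that was resected or ablated during the initial treatment session through the final follow-up visits".
- Section 4.4: "Percentage of Barrett's esophagus resected or ablated during the initial treatment session through the final follow-up visits".
- Section 7.6, as the hypothesis: "The percentage tissue removal of Barrett's metaplasia will be greater for those treated with EndoRotor® than for those treated with control".

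Section 5.6 gives the measurement: "percent reduction of the area with Barrett's esophagus will be determined by a decrease in overall length". It continues: "Using the Prague criteria, both the circumference and maximal length of the Barrett's segment will be estimated". The calculation is then: "A percentage reduction in the length will be calculated by length measured at the follow up endoscopy divided by the total prior length". Overall length is not defined, though it reads most naturally as maximal length. Nothing says how the circumferential measure is used.

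For a circumferential lesion in the EndoRotor arm, section 5.5.3 says "the endoscopist shall resect no greater than 270 degrees of the radial circumference of the esophagus to avoid stricture formation". Sections 5.6.1 and 5.7.2 to 5.7.4 repeat the limit, and section 5.8.1 notes that "the patients are only receiving treatment on up to 270 degrees of surface area to avoid risk of stricture". For the control arm, section 5.5.3 leaves the choice of RFA or cryotherapy to the investigator and the technique to the manufacturer's instructions. It states no circumferential limit.

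The endpoint is tested by a Wilcoxon rank-sum test (7.4, 7.8), and only if non-inferiority and then superiority on the primary endpoint have succeeded (7.8.3).

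**The concern.** Length has one dimension and area has two. Length can stand in for area if treatment clears whole circumferential levels, or if the disease is a narrow tongue. It fails when treatment removes most of the circumference and leaves a strip running along the segment, which is the pattern that the 270-degree limit can produce. The tallest remaining Barrett's is then as long as before.

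The consequence is an internal contradiction. Sections 5.6 and 5.8.1 judge response on biopsies from treated areas, and two consecutive negative rounds make a complete responder. An EndoRotor subject whose treated sector stays negative could therefore be a primary success and score 0% on the secondary endpoint. It is a possibility rather than a certainty, because section 4.3.1 also names visual appearance and does not say how a visible untreated strip counts.

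This is the only secondary endpoint with a hypothesis and a place in the testing sequence, so a result on it would be read as a statement about tissue removed.

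**Working it through.** The plan gives no effect size, standard deviation or power for the secondary endpoint, so there is no planned figure to reproduce. The power figures in 4.7 and 7.3 concern the primary endpoint and are not affected. The check is geometric.

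**Inputs from the documents.** Resection of at most 270 of 360 degrees, or three quadrants of four (5.5.3). Residual length 1 to 6 cm at entry (4.12).

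**Assumptions for illustration.** The segment shapes below; resection over the full length; treated tissue heals clean; untreated tissue stays as it was.

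**Formulas.** Area in quadrant-centimetres (qcm) = sum over 1 cm levels of quadrants with Barrett's. Reduction = 100 × (index − final) / index, for area and for length alike.

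**Case A: 4 cm, fully circumferential.**
- Index area 4 × 4 = 16 qcm. Treated 4 × 3 = 12. Remaining 4 × 1 = 4.
- Whole segment: (16 − 4)/16 = 75%. Treated area only: 12/12 = 100%.
- Maximal length: (4 − 4)/4 = 0%. Circumferential length: (4 − 0)/4 = 100%.
- The 75% does not depend on segment length: 1 − 90/360 = 75%.

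**Case B: 2 cm circumferential plus a one-quadrant tongue to 4 cm.** Index area 2 × 4 + 2 × 1 = 10 qcm.
- Tongue inside the resected sector: remaining 2 × 1 = 2. Area (10 − 2)/10 = 80%; maximal length (4 − 2)/4 = 50%.
- Tongue outside it: remaining 2 + 2 = 4. Area (10 − 4)/10 = 60%; maximal length (4 − 4)/4 = 0%.
- Circumferential length goes from 2 to 0 cm either way: 100%.

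**Case C: 4 cm tongue, one quadrant wide, fully resected.** Area goes from 4 to 0 qcm: 100%. Maximal length goes from 4 to 0 cm: 100%. Circumferential length is 0 at index, so its percentage reduction is undefined.

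| Case | Whole-segment area | Treated area | Maximal length | Circumferential length |
|---|---|---|---|---|
| A | 75% | 100% | 0% | 100% |
| B, tongue resected | 80% | 100% | 50% | 100% |
| B, tongue left | 60% | 100% | 0% | 100% |
| C | 100% | 100% | 100% | undefined |

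Maximal length matches an area figure only in case C. Circumferential length agrees with treated area in cases A and B, but cannot be computed for a tongue and overstates whole-segment removal.

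A separate point in the same sentence of 5.6: follow-up length divided by prior length is the fraction remaining. Taken literally, case A gives 4/4 = 100%, which is opposite in direction to the hypothesis in 7.6.

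**The case against.** Several counter-arguments have force.

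**The reference value is ambiguous.** The endpoint refers to the area that was resected or ablated in the first session, which suggests the treated area as denominator; the formula's total prior length suggests the whole segment. A reader might take 75% as the true value in case A, and so regard circumferential length as 25 points too high. That holds only on the whole-segment reading. On either reading, 0% is wrong.

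**The circumferential measure is collected.** A reader might infer that the planned endoscopy cannot register a 270-degree resection. It can: the Prague circumferential value would fall to zero. The defect is that the scoring rule does not use it.

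**The strip may not persist.** Up to two treatments are allowed (4.2), and 5.7.2 to 5.7.4 provide for resecting visible lesions at later visits. Section 5.8.1 points the other way, limiting further treatment to positive biopsies within the treated segment. The sections must be reconciled; until then, persistence is an assumption.

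**Bias between arms.** Because the limit is stated for one arm only, a reader might infer that length scoring works against EndoRotor, or for it if circumferential length is used. The documents do not support either. Control technique rests on instructions outside them, and a missing limit does not show that control treats the full circumference.

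**Length is used elsewhere.** It defines RFA failure (4.2), eligibility (4.12) and a model covariate (7.4), and it works for tongues. This would support an endpoint called reduction in length. It does not support calling that endpoint area or tissue removal.

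**Limited reach.** The test is reached only after two primary successes, and the primary analysis and sample size are untouched. Both are true, and they limit the importance of the point.

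**Conclusion.** Wrong as written. A stated rule gives a wrong answer for a lesion type that the protocol expressly plans for: 0% on maximal length, where 75% of the whole segment or 100% of the treated area has gone. These figures assume a fully circumferential segment, full-length 270-degree resection, clean healing and an untreated residual strip. The discrepancy is smaller or absent for mixed and tongue-shaped disease.

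The finding applies to the individual score and to what the test can be said to show. Its effect on the arm comparison depends on the share of circumferential lesions, later treatment of the strip and control technique. The documents settle none of these, so no point shift and no direction of bias should be attached to it.

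**What to change.** In section 5.6, replace the length rule with a visual area score applied identically in both arms. At the index and final surveillance endoscopies, record the number of quadrants with Barrett's (0 to 4) at each 1 cm level, and define reduction = 100 × (index − final) / index in quadrant-centimetres. This also corrects the direction of the formula. The score can be taken from the index video (5.5.3) and the digitally saved endoscopies (5.7). It should not depend on a whole-segment biopsy map, because 5.6 and 5.8.1 describe sampling of treated areas and do not establish one.

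State one denominator, treated area or whole segment, and use it throughout 4.4, 5.6 and 7.6; report the other as supportive. The grid should mark the quadrants treated in the first session so that both can be computed. The choice has consequences: on the whole-segment denominator, a fully circumferential segment treated once cannot exceed 75% in the EndoRotor arm. Keep the changes in Prague circumferential and maximal length as descriptive.

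If the sponsor prefers to keep length, rename the endpoint and the 7.6 hypothesis as reduction in maximal length, and make no claim about area or tissue removed.

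Separately, 5.7.2 to 5.7.4 and 5.8.1 must be reconciled on what is treated at later visits.

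Cost: one extra CRF grid, slightly more recording time and SAP wording. No extra endoscopy or biopsy, and no change to the primary sample size.

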4.12 Inclusion Criteria

Candidates for this study must meet **ALL** of the following Inclusion criteria:

1. Subjects who are ≥ 30 and < 79 years of age; inclusive of males and females.
2. Subjects with a history of confirmed Barrett's esophagus with dysplasia (low-grade or high-grade) refractory to radiofrequency ablation 3 times.
3. Residual Barrett's length is ≥ 1 cm and ≤ 6 cm.
4. Histologic persistence of intestinal metaplasia (any non-squamous epithelial lesion) following treatment and failed eradication.
5. Following 3 failed RFA procedures with no confirmed evidence of EAC and having confirmed no endoscopic and histologic evidence of EAC at the time of therapy.
6. Subject capable of giving informed consent.
7. Subject has a reasonable expectation for prolonged survival (greater than 5 years).
8. Subject can tolerate repeated endoscopic procedures.
9. Absence of strictures that preclude the passage of the endoscope.
10. Subjects with the ability to understand the requirements of the study, who have provided written informed consent, and who are willing and able to return for the required follow-up assessments through 6 months or 9 months, as indicated.

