7.0 STATISTICAL METHODS

7.1 General Principles

By-subject listings will be created for each CRF module. Summary tables for continuous variables will contain the following statistics: N, mean, median, standard deviation, minimum, maximum, and 95% confidence interval (CI) as appropriate. Summary tables for categorical variables will include N, percentage, and 95% CIs on the percentage. CIs for proportions will be calculated using the Clopper- Pearson exact method. Graphical techniques will be used when such methods are appropriate and informative. Tables will separate data by treatment arm.

Transformations of the data may be explored if warranted by the distribution of the data. Analyses resulting from transformations applied after the data are unmasked will be considered to be exploratory.

Unless otherwise specified, all analyses will be 2-sided at the 0.05 level of significance. All analyses will be performed using SAS® (Version 9.4) and graphs using R, version 3.3.1 or later, or using SAS®.

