7.3 Sample Size

Assuming a response rate for Barrett's esophagus with EndoRotor® ablative therapy of 80%, and for cryoablation of 50%, the study will have over 95% power to demonstrate non-inferiority (NI), given a NI delta of 10%, of EndoRotor® to cryoablation and will have 91.6% power to demonstrate superiority of EndoRotor® over continued ablative therapy using a sample size of 110 evaluable subjects, 55 in each treatment group.

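### The section 5.6 formula for percentage reduction gives the percentage of Barrett's length remaining, the reverse of the removal scale in sections 7.5 and 7.6

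*Combined protocol and SAP*

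**What the plan says.** The Protocol Summary words the secondary endpoint as "Percent reduction of the area with Barrett's esophagus that was resected or ablated during the initial treatment session through the final follow-up visits". Section 4.4 words it as "Percentage of Barrett's esophagus resected or ablated during the initial treatment session through the final follow-up visits". Section 5.6 repeats the Protocol Summary wording and makes it operational in two statements. The first is that "percent reduction of the area with Barrett's esophagus will be determined by a decrease in overall length". The second, after a reference to the Prague criteria, is the calculation: "A percentage reduction in the length will be calculated by length measured at the follow up endoscopy divided by the total prior length".

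The statistical sections take the endpoint over without redefining it:

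- Section 7.4 compares percentage reduction between arms with a Wilcoxon rank-sum test.
- Section 7.5 sets the sensitivity rules for missing values. The best case gives missing EndoRotor subjects 100% removal and missing controls 0%; the worst case does the opposite. If the two disagree, the imputed values are moved in 1% steps until the conclusion changes.
- Section 7.6 defines the parameters as mean percentage of tissue removed, with the alternative that the EndoRotor mean exceeds the control mean.
- Section 7.8.3 tests this endpoint last, after non-inferiority and superiority on the primary endpoint.
- Section 7.1 sets the sidedness: "Unless otherwise specified, all analyses will be 2-sided at the 0.05 level of significance".

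**The concern.** Follow-up length over prior length is what is left, not what has gone. The formula therefore contradicts its own label, the statement before it in section 5.6, the imputation values in section 7.5 and the hypothesis in section 7.6. No passage contains a step that subtracts the ratio from 1 or from 100.

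The endpoint is formally tested, and a programmer working to specification has no other formula. The error would also be silent, because every value still looks like a plausible percentage. At stake are the reported arm summaries, the sign of the treatment effect against the section 7.6 alternative, and the labels on the missing-data analyses.

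A smaller gap sits in the same sentence: the prior length is not tied to a visit. The endpoint title, which runs from the initial treatment session to the final follow-up visits, points to the endoscopy before the index procedure. If the preceding visit were meant, a subject clear at both 3 and 6 months (Scenario 1, section 5.7.1.1) would give 0/0.

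**Working it through.** **The plan's own figure.** No power or sample size is stated for the secondary endpoint. The nearest stated figure is 91.6% power for primary superiority (section 7.3: 80% against 50%, 55 per arm). A two-sided 0.05 normal approximation with pooled null variance gives 92.1%, which is close enough to confirm how the planning rates are meant. Nothing below depends on it.

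**Step 1: the formula.** Let L0 be the prior length and L1 the follow-up length.

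- Section 5.6 score: S = 100 × L1/L0
- Reduction: R = 100 × (L0 − L1)/L0 = 100 − S

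The two agree only at 50%. For L0 = 4 cm, within the 1 to 6 cm entry range of section 4.12:

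| L1 (cm) | S, as written | R, reduction |
|---|---|---|
| 0 | 0% | 100% |
| 1 | 25% | 75% |
| 2 | 50% | 50% |
| 4 | 100% | 0% |

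**Step 2: complete data, illustrated.** The section 7.3 rates give 0.80 × 55 = 44 EndoRotor responders and 0.50 × 55 = 27.5 control responders, rounded down to 27. My assumptions are that responders have 0 cm left (R = 100) and non-responders have R = 50.

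- Mean R, EndoRotor: (44 × 100 + 11 × 50)/55 = 90.0%
- Mean R, control: (27 × 100 + 28 × 50)/55 = 74.5%
- As written these read 10.0% and 25.5%, and the EndoRotor median reads 0% instead of 100%.
- Mann-Whitney U for EndoRotor on R: 0.5 × 44 × 27 + 44 × 28 + 0.5 × 11 × 28 = 1980
- U on S: 55 × 55 − 1980 = 1045
- Two-sided p (normal approximation with tie and continuity corrections): 0.00075 on both scales

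The p-value is the same, but the direction is opposite. The probability that an EndoRotor value exceeds a control value, with ties counted half, is 1980/3025 = 0.655 on R and 1045/3025 = 0.345 on S.

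**Step 3: missing data, illustrated.** The enrolment plan is 120 subjects with 10 lost (section 4.5). I assume an even split and add 5 imputed values per arm to the 55 observed. Mixed means section 7.5 removal values combined with observed section 5.6 ratios. Differences are EndoRotor minus control means, in percentage points.

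| Analysis | One scale (removal) | Mixed scales |
|---|---|---|
| Best case | +22.50, U = 2487.5, p = 0.00002 | −5.83, U = 1510, p = 0.072 |
| Worst case | +5.83, U = 2090, p = 0.072 | −22.50, U = 1112.5, p = 0.00002 |

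The swap is exact. The mixed best case holds observed values 100 − R, with 100 imputed for EndoRotor and 0 for control. Subtracting every value from 100 gives R, with 0 for EndoRotor and 100 for control, which is the one-scale worst case. So U becomes 3600 − 2090 = 1510 and the sign reverses. The multiple-imputation analysis does not mix scales, because it imputes from the observed values.

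**Step 4: varying the assumptions.**

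- Non-responder reduction from 25% to 75%: the one-scale best case runs from +29.58 to +15.42 and the worst case from +12.92 to −1.25, with U and p unchanged.
- 28 control responders instead of 27: p = 0.0014 observed, 0.00004 one-scale best and 0.10 one-scale worst, again swapped when mixed.
- A quarter of EndoRotor responders (11 of 44) with a 50% reduction instead of full clearance: the observed difference falls to +5.5 points and p rises to 0.25.

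The group figures therefore depend on the assumed outcomes; the reversal does not.

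**The case against.** The strongest reply is that this is a drafting slip with an obvious intent. The sentence itself names its result a reduction, and every other description of the endpoint speaks of reduction, resection, ablation or removal. Harm requires a programmer to follow one sentence in a procedures section against its own label and against the statistical sections.

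The inferential effect is also small. The main two-sided p-value is identical on either scale. The sensitivity damage needs missing data, section 5.6 coding and uncorrected section 7.5 values together. Even then the pair of p-values (0.00002 and 0.072) is the same, so on significance the trigger for a tipping-point analysis fires in both cases. The endpoint is reached only if both primary tests succeed.

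The group illustration is fragile too. EndoRotor treatment of a circumferential lesion is limited to 270 degrees (section 5.5.3), and only biopsies in the treated segment lead to further treatment (section 5.8.1). A responder may therefore keep some Barrett's length.

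Most of this stands as a limit on size: the intent is clear, the p-values survive, and the group figures are illustrations. It does not rescue the formula, which is the only one given. Unchanged p-values do not protect the reported means and medians, the direction against section 7.6, or the meaning of the best-case and worst-case labels. Naming the visit and the length is a separate clarification, but a corrected formula cannot be programmed without it.

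**Conclusion.** The point holds. As written, the section 5.6 formula returns 100 minus the percentage reduction for every subject, opposite to the scale of sections 7.5 and 7.6. This follows from the formula alone and needs no assumption.

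The consequences are limited to the secondary endpoint. Coded as written, the summaries and the direction of effect reverse; in the illustration, 90.0% against 74.5% reads as 10.0% against 25.5%. With complete data and a single baseline per subject, the two-sided test result is unchanged. If data are missing and the two scales are combined, the best and worst cases exchange places with reversed sign and the tipping-point steps run from the wrong end. The group figures rest on the assumed clearance of responders, the assumed partial reduction of non-responders and the assumed 5 missing per arm. Power, sample size and the primary analysis are not affected. The formula should be corrected before the secondary analysis is programmed.

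**What to change.** Replace the section 5.6 sentence with: percent reduction = 100 × (baseline length − length at the final follow-up endoscopy) / baseline length. Three details are needed to make it programmable:

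- **Baseline visit.** Name the endoscopy before the index procedure. Section 5.5.3 already calls for endoscopic treatment "with outpatient video documentation of the residual Barrett's changes during upper endoscopy".
- **Length used.** Use the same residual length as inclusion criterion 3 ("Residual Barrett's length is ≥ 1 cm and ≤ 6 cm"). The sponsor should confirm that this is the Prague maximal length, since a circumferential length can be 0 and cannot then serve as a denominator.
- **No usable baseline.** Criterion 3 guarantees a length above 0 only for eligible subjects. State how a randomised subject without one is handled in the intent-to-treat analysis.

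Use the same definition in the Protocol Summary and in sections 4.4, 5.6 and 7.4 to 7.6.

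The cost is one formula, one named visit, one sponsor confirmation and matching wording. Lesion length is already needed for eligibility and as a covariate in section 7.4, so using it adds no measurement. That cannot be said of a baseline circumferential length: neither the section 5.1.1 baseline list nor the Appendix 1 schedule names a Prague measurement.
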